9.4.3 Sensitivity and Supplementary Analyses for Secondary Efficacy Endpoints

Additional sensitivity analyses may be performed as needed to assess impact of missing data for secondary endpoints due to a pandemic or natural disaster.

9.4.4 Supportive Secondary Efficacy Endpoints and Analyses

Not applicable.

9.5 Additional Efficacy Analyses

For both the US FDA and EU regulatory agencies, analyses for additional efficacy endpoints will be performed on the ITT population using data as observed. The additional efficacy endpoints are listed in [Section 3.3](#).

9.6 Efficacy Subgroup Analyses

For the primary and key secondary endpoints, analyses will be conducted using the following subgroups and descriptive summary statistics provided:

Analyses will be conducted using the following subgroups:

- Sex (Female, Male)
- Age group (<65, \geq 65 years)
- Race (White, non-White)
- Ethnicity (Hispanic or Latino, not Hispanic or Latino)
- Region (North America, EU)

- Baseline FWS at maximum frown (moderate, severe)
- Baseline FLO-11 total score (transformed) \leq 50
- Fitzpatrick skin type (Types I & II, Types III & IV, Types V & VI)

10.0 Safety Analyses

10.1 General Considerations

Safety data will be summarized for the Safety Population. Safety summaries will be presented by treatment group, by overall study, by study period, and by treatments received in the DB Period and in the OL Period (i.e., AGN-151586/AGN-151586, AGN-151586/None, Placebo/AGN-151586, Placebo/None).

For the safety analysis, subjects are assigned to a treatment group based on the treatment actually received, regardless of the treatment randomized.

The safety parameters will include AEs, vital signs, 12-lead ECGs, laboratory evaluations (hematology and chemistry), neurological assessment (including examination of cranial nerves II through VII), and presence of antidrug antibodies. For change from baseline safety parameters, “baseline” refers to the last non-missing observation before the first study drug administration in the study.

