4 INVESTIGATIONAL PLAN

4.1 Overall Study Design and Plan

This is a 12-week, multicenter, Phase 3 study designed to evaluate the safety and efficacy of AGN-151586 in treating GL. Subjects are adults (≥ 18 years of age) with moderate to severe GL at maximum frown as assessed independently by both the investigator and subject using the FWS. The investigator and subject ratings for GL will be done at the Screening Visit and at the Baseline Day 1 Visit. The investigator and subject ratings must match within a visit but do not have to match between Screening and Baseline Day 1. Each eligible subject may receive up to 2 study treatments with AGN-151586. The time of study treatment administration defines Hour 0 for the treatment period (on Day 1 for double-blind period and on Day 43 for open-label period).

Eligible subjects will be enrolled into the study containing 2 treatment periods:

Double-blind Period: Screening will occur up to 14 days prior to Baseline Day 1. Randomization and treatment will occur on Baseline Day 1 after all other study procedures have been completed. A single treatment of AGN-151586 or placebo will be administered on Baseline Day 1, based on randomization (3:1 ratio of AGN-151586:placebo). Randomization will be stratified by investigator site, toxin use history (for aesthetic purpose), and baseline GL severity at maximum frown. All enrolled subjects will receive treatment on Baseline Day 1 and attend in-clinic site visits to fully characterize the onset of treatment effect. Thereafter, in-clinic site visits will be completed to characterize the peak and duration of effect.

The double-blind period will end on Day 43. The Day 43 visit will occur 42 ± 2 days following the Day 1 visit. The study assessments conducted during the Day 43 visit serve as the final assessment for the double-blind period and as the baseline assessment for the open-label period.

Open-label Period:

For subjects meeting all the retreatment criteria on Day 43, a single open-label treatment with AGN-151586 will be administered on the same day. The subject will then be followed for approximately 6 weeks (through Day 84). The schedule of the follow-up visits in the open-label period is the same as that in the double-blind period. After each study treatment administration, subjects must remain in the clinic for at least 30 minutes for observation of any AEs.

Retreatment is only permitted on the Day 43 visit.

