7.5 Statistical Analyses for Safety

The safety analyses will be performed using the safety population (i.e., Safety Analysis Set). The safety parameters will include AEs, vital sign measurements, 12-lead ECG, laboratory evaluations (hematology and chemistry), neurological assessment (examination to consist of assessment of cranial nerves II through VII), physical examination, and immunogenicity. The last nonmissing safety assessment before study drug administration will be used as the baseline for all analyses of that endpoint.

Treatment-emergent AEs are defined as any AE with the onset that is after the first dose of study drug. Events where the onset date is the same as the study drug start date are assumed to be treatment-emergent, unless known to have started prior to study treatment administration.

An overview of AEs will be presented consisting of the number and percentage of subjects experiencing at least one event for each of the following AE categories:

- 1. Any TEAE
- 2. Any TEAE related to study treatment according to the investigator (i.e., study drug-related, study injection procedure-related)
- 3. Any severe TEAE
 - a. Any severe TEAE related to study treatment according to the investigator
- 4. Any serious TEAE
 - a. Any serious TEAE related to study treatment according to the investigator
- 5. Any TEAE leading to discontinuation of study drug
- 6. Any TEAE leading to death
- 7. PDSOT TEAEs
- 8. Neurological assessment TEAEs
- 9. All deaths

Treatment-emergent AEs will be summarized by system organ class (SOC) and PT; by maximum relationship to study treatment (i.e., study drug related, study injection procedure related) as assessed by the investigator (e.g., reasonable possibility or no reasonable possibility) and SOC and PT; by maximum severity and SOC and PT; and by subject number and SOC and PT. Specific treatment-emergent AEs will be counted once for each subject for calculating percentages, unless stated otherwise. In addition, if the same AE occurs multiple times within a subject, the AE will be counted only once, and the highest severity and level of relationship to investigational product will be reported.

Serious AEs (including deaths) and AEs leading to study drug discontinuation will be summarized by SOC and PT and in listing format.

Possible distant spread of toxin PTs will be identified in the SAP and PDSOT TEAEs will be summarized by PT.

Neurological assessment TEAEs will be summarized by PT.

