A subject who is randomized based on a wrong stratum will be analyzed according to the subject's actual stratum. However, if a subject has a baseline FWS lower than moderate severity at maximum frown, then the subject will be included in stratified analyses within the moderate GL severity at maximum frown stratum. In analyses not stratified by baseline FWS, the observed baseline FWS will be used.

For efficacy analyses of FWS assessments, “baseline” refers to the last non-missing observation before either the first administration of study drug or randomization if no study drug is given or the administration of study drug during retreatment. The change

[figure not shown]
from baseline values will be computed as the post-baseline value minus the observed baseline value.

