10.3 Analysis of Laboratory Data

Laboratory evaluations consisting of chemistry and hematology, and changes from baseline at each assessment timepoint will be summarized by treatment group and study period. In addition, potentially clinically important (PCI) laboratory values will be summarized.

Each laboratory value will be summarized for all time points (starting with Baseline) with the number of non-missing observations, mean and standard deviation, median, minimum, and maximum. Mean change from baseline to each applicable post-baseline visit will be summarized for each laboratory parameter, with the number of observations, baseline mean, and visit mean. The change from baseline mean, standard error, and 95% confidence interval will be presented for the mean change from baseline within each treatment group.

Changes in laboratory values will be tabulated using shift tables categorized as low, normal, or high based on the normal ranges of the laboratory used for each sample

[REDACTED]
[REDACTED]
[REDACTED].

Laboratory values will be evaluated [REDACTED]. For each laboratory PCI criterion, the number and percentage of subjects who have a post-baseline laboratory value meeting the criteria will be summarized. [REDACTED]

[REDACTED]
[REDACTED]
[REDACTED].

Listings will be provided to summarize subject-level laboratory data for subjects meeting PCI criteria.

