10.6 Other Safety Analyses

Electrocardiogram (ECG): Descriptive statistics for quantitative ECG parameters (i.e., heart rate, QRS duration, QTcB interval, QTcF interval, RR interval, and PR interval) at baseline, post-baseline, and changes from baseline values at each post-baseline timepoint will be presented.

ECG parameters are considered PCI if ECG values meet either the actual value or change from baseline PCI high criteria [REDACTED]. The number and percentage of subjects with PCI post-baseline values will be tabulated. [REDACTED]

[REDACTED]

[REDACTED]

[REDACTED]

A supportive listing of subjects with PCI post-baseline values will be provided.

Immunogenicity Assessment: Immunogenicity results, manifested as the presence of binding antibodies (positive) and neutralizing antibodies (positive) to AGN-151586, will be summarized in a table for baseline and post-baseline data. Immunogenicity findings (positive) will be tabulated with the number and percentage of subjects at each visit separately for each treatment group. Percentages will be based on the number of treated subjects with interpretable antibody assays in each treatment group at the specified visit.

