14.0 Version History

Table 3. SAP Version History Summary

Version	Date	Summary
1.0	20 May 2021	Original version
2.0	15 February 2022	
Updated study design, primary and secondary efficacy endpoints and estimand attributes for US and EU regulatory agencies, removed mITT population
 
Updated hierarchical testing sequences with included/excluded endpoints
 
[REDACTED]
 
Added safety assessments for neurological assessment, ECG assessments, and laboratory assessments
 
Updated sample sizes
 
Added PCI criteria for laboratory, vital signs, and ECG

3.0	15 November 2022	
Updated key secondary, secondary, and other efficacy endpoints and estimand attributes for US and EU regulatory agencies
 
Updated specifications for the multiple imputation analysis method
 
Updated efficacy analyses to include GAC-GL and responder definition
 
[REDACTED]
 
[REDACTED]
 
Clarified baseline definition and retreatment baseline definition for FWS-related efficacy analyses and safety analyses
 
Clarified that FLO-11 total scores refer to the transformed scores
 
Updated safety analyses to include TEAE onset and duration analyses, and frequent TEAE analyses
 
Updated PDSOT terms and PCI criteria in appendices

4.0	23 November 2022	Updated primary and key secondary endpoints and estimands for US: Grade 0 or 1 (none or mild) and at least a 2-grade improvement

Version	Date	Summary
5.0	08 April 2023	
Removed gatekeeping strategy from sample size section
 
[REDACTED]
 
Clarified that the 95% confidence interval would be based on the responder rate differences
 
[REDACTED]
 
[REDACTED]
 
[REDACTED]
 
[REDACTED]
 
Removed FWS at baseline from the multiple imputation model
 
Added other efficacy analyses to be performed for other efficacy endpoints
 
Updated baseline characteristics to include FWS at maximum frown as assessed by investigator and by subject
 
Removed vital signs shift tables
 
Updated MedDRA versioning to be the version used for the study at the time of database lock
 
[REDACTED]
 
[REDACTED]

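### SAP 10.1 measures open-label safety changes from before the first dose in the study, while protocol 4.1 names Day 43 as the open-label baseline; for Placebo/AGN-151586 the two periods are combined

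*SAP*

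**What the plan says.** SAP 10.1 governs all safety changes. Baseline there "refers to the last non-missing observation before the first study drug administration in the study". The safety analysis set in protocol 7.2 treats both AGN-151586 and placebo as study drug, so for every treated subject this is the value before the Day 1 injection.

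That baseline is carried into the open-label period. SAP 10.1 presents safety by study period and "by treatments received in the DB Period and in the OL Period". For laboratory data, SAP 10.3 says that "changes from baseline at each assessment timepoint will be summarized by treatment group and study period", and SAP 10.4 does the same for vital signs. SAP 10.6 tabulates ECG changes at each post-baseline timepoint, and an ECG value can be flagged as potentially clinically important (PCI) if it meets "either the actual value or change from baseline PCI high criteria".

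Protocol 4.1 says that the Day 43 assessments "serve as the final assessment for the double-blind period and as the baseline assessment for the open-label period", with no exception for safety. Protocol 7.5, the safety-analysis section, says: "The last nonmissing safety assessment before study drug administration will be used as the baseline for all analyses of that endpoint". It does not state whether the first dose or the retreatment dose is meant.

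For the Facial Wrinkle Scale (FWS), SAP 9.1 does provide a second baseline, with the words "or the administration of study drug during retreatment".

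**The concern.** The open-label period has no control group (protocol 4.2). Placebo/AGN-151586 is the only sequence in which the open-label injection is a first active exposure. With the SAP baseline, the open-label change in that sequence starts about six weeks before the subject receives any AGN-151586 and runs through the whole placebo period. A shift that arose on placebo and persisted would appear in the open-label tables. An ECG change flag already met on placebo could be counted again after the AGN-151586 dose.

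The SAP resets the clock elsewhere: FWS has a retreatment baseline, and SAP 10.2.1 counts onset from the most recent dose for distant-spread and treatment-related adverse events. Laboratory, vital-sign and ECG changes are not reset.

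**Working it through.** **No stated figure to reproduce.** The point concerns a definition. The only document number used is the allocation in SAP 2.4: 600 at 3:1 gives 600 × 3/4 = 450 and 600 × 1/4 = 150. The affected group is therefore at most about 150 subjects (25%), reached only if every placebo subject is retreated.

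**What is mixed.** For a Placebo/AGN-151586 subject at an open-label visit,

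visit − Day 1 = (Day 43 − Day 1) + (visit − Day 43).

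The first term is change on placebo; the second is change after the first AGN-151586 dose. If AGN-151586 has no effect and the parameter is otherwise stable after Day 43, the expected change is zero from a Day 43 baseline and equals the whole placebo-period drift from the SAP baseline. For AGN-151586/AGN-151586 both terms are change on active drug, so nothing from placebo enters.

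**Illustration 1: drift in the mean (all values assumed).** Normal model, visit SD 1, n = 150, no drug effect, equal correlation ρ between visits. SE = √(2(1 − ρ)/150), which is 0.082 for ρ = 0.5 and 0.063 for ρ = 0.7. SAP 10.3 and 10.4 plan a within-group 95% confidence interval for the mean change. The probability that it excludes zero under the SAP baseline is:

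| Placebo-period drift (SD) | ρ = 0.5 | ρ = 0.7 |
|---|---|---|
| 0 | 0.05 | 0.05 |
| 0.1 | 0.23 | 0.35 |
| 0.2 | 0.69 | 0.89 |
| 0.3 | 0.96 | 1.00 |

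From a Day 43 baseline it is 0.05 in every row. The documents give no reason to expect any particular drift.

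**Illustration 2: flags already met on placebo (all values assumed).** No drift; correlation 0.7 between visits six weeks apart and 0.6 between visits twelve weeks apart; a flag is an increase of 1.5 or 2.0 between-subject SD.

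- SD of change is √(2(1 − ρ)): √0.6 = 0.775 over six weeks and √0.8 = 0.894 over twelve. The ratio is 1.15, so the SD is 15% larger from Day 1. With 0.7 at both intervals the ratio is 1.00.
- Covariance of the Day 43 and open-label changes, both from Day 1, is 0.7 − 0.6 − 0.7 + 1 = 0.4. Their correlation is 0.4/√(0.6 × 0.8) = 0.577.
- Threshold 1.5: P(flag) = 1 − Φ(1.5/0.894) = 0.0468, or 7.0 of 150. The bivariate normal probability that the flag was also met at Day 43 is 0.0090. That is 19.3% of flags, or 1.35 of 150.
- Threshold 2.0: P(flag) = 1 − Φ(2.0/0.894) = 0.0127, or 1.9 of 150. The joint probability is 0.0012. That is 9.7% of flags, or 0.18 of 150.
- With correlations of 0.8/0.7 or 0.6/0.5, the share ranges from 4.4% to 24.4% and the count from 0.03 to 2.4 of 150.

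These counts are per parameter per visit. The text left visible mentions change-based flags only for ECG; the ECG thresholds and part of the laboratory and vital-sign criteria are redacted.

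**The case against.** The strongest defence is that protocol 7.5, not 4.1, governs safety analysis. It names no Day 43 baseline and sets one baseline for all analyses of an endpoint, so SAP 10.1 can be read as making it precise. The choice also looks deliberate: SAP 14.0 records for version 3.0, "Clarified baseline definition and retreatment baseline definition for FWS-related efficacy analyses and safety analyses". A single untreated baseline is a recognised convention, and in AGN-151586/AGN-151586 it shows cumulative change on active drug. This stands in part. The separate FWS rule is no evidence of oversight, and the SAP does not plainly contradict the whole protocol. But protocol 4.1 makes no exception for safety, and the visible version history does not say why the SAP departs from it.

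A reader might infer that placebo-period changes are reported as an AGN-151586 effect. The documents do not support that. Placebo/AGN-151586 is a separate column, double-blind changes are also tabulated, and any parameter measured at Day 43 has its placebo-period mean change on view. What a reader cannot recover from two group means is the spread and confidence interval of the within-subject change after Day 43, or which flagged subjects are new.

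Nor is change from baseline shown to be the main open-label safety evidence: adverse events, distant-spread and neurological events, PCI values and antibodies are also planned.

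Finally, the content of the activity schedule is not available, so it cannot be confirmed that every safety parameter is measured at Day 43. A baseline worded as the last value before that dose still works, but it may fall on an earlier visit.

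**Conclusion.** The point holds as a minor improvement. Protocol 4.1, protocol 7.5 and SAP 10.1 do not give one clear open-label safety baseline. Under the SAP rule, open-label changes in Placebo/AGN-151586 combine placebo-period change with change after first active exposure. This affects at most about 150 subjects, and only change-from-baseline summaries, laboratory shift tables and change-based flags. Efficacy and type I error are untouched.

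The size cannot be computed from the documents. In the assumed base case (correlations 0.7 and 0.6), about 0.2 to 1.4 of 150 subjects per parameter per visit carry a flag already met on placebo. The corresponding share, 10% to 19% of flags, sounds larger only because flags are rare. The 15% larger SD depends entirely on correlation falling with time and vanishes if it does not. The drift results show what a given drift would do, not that one will occur.

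**What to change.** In SAP 10.1, for open-label change, shift and change-based PCI summaries, add a baseline defined as the last non-missing value before the Day 43 dose, at least for Placebo/AGN-151586. Keep the pre-first-dose baseline for double-blind and overall-study summaries, so that cumulative change in AGN-151586/AGN-151586 is still shown. Align protocol 4.1 and 7.5 with this. If the sponsor prefers a single safety baseline, the minimum is to say in all three places that the pre-first-dose value is intended for both periods, and why.

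The cost is one SAP sentence, a second baseline flag in the analysis datasets, and one more set of open-label laboratory, vital-sign and ECG tables. No new data are needed.

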10.2 Adverse Events

Adverse events (AEs) will be summarized and presented using primary MedDRA System Organ Classes (SOCs) and preferred terms (PTs) according to the version of the MedDRA coding dictionary used for the study at the time of database lock. The actual version of the MedDRA coding dictionary used will be noted in the AE tables and in the clinical study report. Specific adverse events will be counted once for each subject for calculating percentages, unless stated otherwise. In addition, if the same adverse event occurs multiple times within a subject, the highest severity and level of relationship to investigational product will be reported.

10.2.1 Treatment-Emergent Adverse Events

Treatment-emergent AEs (TEAEs) are defined as any AE with the onset that is after the first dose of study drug. Events where the onset date is the same as the study drug start date are assumed to be treatment-emergent, unless known to have started prior to study

treatment administration. All TEAEs will be summarized overall, as well as by primary MedDRA SOC and PT. The SOCs will be presented in alphabetical order, and the PTs will be presented in alphabetical order within each SOC. The number and percentage of subjects experiencing treatment-emergent AEs will be summarized.

In addition, for both possible distant spread of toxin (PDSOT) TEAEs and treatment-related TEAEs, onset after study drug administration and duration will be evaluated. TEAE onset will be reported by number of days subsequent to the most recent study drug administration and will be summarized with descriptive statistics. TEAE duration will be defined as ((end date minus start date) + 1 day) and will be summarized with descriptive statistics.

10.2.2 Adverse Event Overview

An overview of AEs will be presented consisting of the number and percentage of subjects experiencing at least one event for each of the following AE categories:

- Any TEAE
- Any TEAE related to study treatment according to the investigator
 - Any TEAE related to study drug according to the investigator
 - Any TEAE related to study procedure according to the investigator
- Any mild TEAE
 - Any mild TEAE related to study treatment according to the investigator
- Any moderate TEAE
 - Any moderate TEAE related to study treatment according to the investigator
- Any severe TEAE
 - Any severe TEAE related to study treatment according to the investigator
- Any serious TEAE
 - Any serious TEAE related to study treatment according to the investigator
- Any TEAE leading to discontinuation of study drug
- Any TEAE leading to death

- Any PDSOT TEAE
- Any neurological assessment associated TEAE
- All deaths

10.2.3 Treatment-Emergent Adverse Events by SOC and/or PT

TEAEs will be summarized by SOC and PT; TEAEs considered related to study treatment as assessed by the investigator (i.e., reasonable possibility) by SOC and PT; by maximum severity by SOC and PT; and listed by subject number by SOC and PT. Specific adverse events will be counted once for each subject for calculating percentages, unless stated otherwise. In addition, if the same adverse event occurs multiple times within a subject, the adverse event will be counted only once and the highest severity and level of relationship to study drug will be reported.

In addition, TEAEs will be summarized by PT and sorted by decreasing frequency for the total active group after first dose of AGN-151586. Frequent TEAE incidence will be reported for PTs with $\geq 5\%$ subject incidence, listed by SOC and PT.

